The Effect of Temporal Muscle Suspension on the Risk of Temporal Hollowing:
A Prospective Randomized Clinical Trial

[name]
Associate Professor
Department of Plastic and Reconstructive Surgery
Johns Hopkins School of Medicine

Johns Hopkins Hospital
[name]
[name]
[contact]
[contact]

Application No. : IRB00120812

The pterional approach to the cranio-facial region is an often-used approach by neurosurgeons. This surgical approach is used for access to intra-cranial abnormalities (ie. Tumors, trauma, or vascular insults). Temporal hollowing is a common complication that that can affect the patient both physically and emotionally. In an aesthetic region, it can represent a stigma of disease that prevents the patient from moving on with the normalcy of their disease-free lives. The hollowing generally occurs within 6 months from the index surgery. Currently the exact mechanism or incidence of this complication is not very well described.

The purpose of this prospective study is see if traditional techniques to the closure and temporal muscle suspension (TMS) after the pterional approach will show any differences in post-operative temporal hollowing (TH).

1. Objectives

The primary objective is to identify which patients undergoing a traditional pterional approach with 2 different surgical techniques for TMS will develop TH. Pre and post-operative CT scans will be reviewed and analysis with previously proven metrics will be performed.

2. Background

Surgical Details/Anatomy

The pterional approach is an indicated neurosurgical approach commonly used for anterior circular aneurysms, suprasellar lesions, and medial sphenoid wing tumors (1,2). A curvilinear incision from the midline widows peak and extending laterally to 1 cm anterior to the tragus of the ear, terminating within a skin crease, with preservation of the superficial temporal artery if possible. The temporalis fascia is encountered and divided. Either the entire temporalis muscle can be elevated or a cuff of temporalis muscle can be left on the cranium to facilitate closure and suspend the temporalis muscle. Subperiosteal dissection of the muscle is performed and the craniotomies are then accomplished. Reconstruction of the pterional approach can be accomplished with bony fixation of the bone flap. However, the TMS can be performed by:

Date: 10/24/2017
Principal Investigator: [name]
Application Number: IRB00120812

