1. Resuspension of the temporalis muscle to the cuff of muscle left on the temporal crest
or
2. Suturing the temporalis muscle directly to one of the bone plates that is used to for
fixation.

Current Literature

The TH can occur either due to direct injury to the muscle, atrophy from denervation or even loss of vascular supply (3). Modern neurosurgical techniques have led to great improvements of surgical and functional outcomes, however less attention has been paid to the post-operative complications of scarring and soft tissue deformities (4). There have been several techniques and alterations to the traditional pterional approach to overcome some of the surgical drawbacks such as TH. The most common published is the use of a minipterional (MPT) approach (5). However, the minimalist approach has been debated regarding its effectiveness due to the narrowing of the visual field and restricted maneuverability (6). In the Johns Hopkins experience a retrospective review performed by Huang et al. found the MPT a suitable alternative approach without suboptimal visualization and no instances of improper vascular clip applications (7). They also described limited temporal wasting in 96% of their patients. The obvious limitations to this study and much of the studies in the literature are that they are retrospective in design. Additionally, the primary objective of that study was to evaluate the safety and efficacy of a minimalist approach. To their credit the temporal hollowing was addressed with a placement of an artificial implant. To date there has not been a prospective study regarding the reconstructive placement of the bone flap and temporalis muscle after a pterional approach to the cranium. Elucidation of a surgical cause of TH may lead to a decrease in secondary surgeries and the inherit risks that are associated.

3. Study Procedures

This study will include all patients under the care of [name] MD who qualify for a pterional approach for management of their neurosurgical disease. A pre-operative CT scan will be performed using the Gordon/Stryker Maxillofacial protocol, which is performed as part of the patients routine workup. If

Date: 10/24/2017
Principal Investigator: [name]
Application Number: IRB00120812

the patient agrees to take part in the study, the patient will be randomized into 1 of 2 groups (randomization will take place by a coin flip).

Group Heads: Traditional pterional approach with a muscle cuff left for TMS

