Group Tails: Traditional pterional approach with TMS performed with a bone plate.

All patients will be assigned a confidential experimental number which will be linked to their MRN. The linking database identifying patients with their alphanumeric code will be stored on a single computer that is password protected. The password will only be given to the Co-Investigators on this IRB application.

Routine follow up will be performed at 1 week from surgery, 1 month, and lastly 6 months from surgery where a routine post-operative CT Scan will be performed.

Photographs will be taken on the lateral head for comparison. All identifying markers (eyes, nose, and lips, or skin lesions/tattoos) will be removed for privacy. All other care and services will be as per routine.

There will be no extra research procedures performed or asked of the patient.

Demographic data including age, gender, indication for surgery, length of surgical time, and complications will be recorded.

a. Study Duration

- a. The duration of the study will conclude 6 months after the last patient is enrolled. The study does not alter the normal amount of post-operative visits that are considered routine.

b. Blinding, including justification for blinding or not blinding the trial, if applicable.

There will be no blinding of the study as the operating surgeon will need to know which operation to perform.

c. Justification of why participants will not receive routine care or will have current therapy stopped.

- a. All patients enrolled will receive routine care

d. Justification for inclusion of a placebo or non-treatment group.

- a. There will be no role for a placebo group or a non-treatment group, as standard of care is some form of TMS

e. Definition of treatment failure or participant removal criteria.

- a. Participant removal will be initiated if they are unwilling to follow up in a routine fashion as outlined in the study protocol.

f. Description of what happens to participants receiving therapy when study ends or if a participant's participation in the study ends prematurely.

- a. All patients under the care of [name] will receive routine care and followup. This includes management of all surgical complications. There is no alteration of their routine care when the study ends or is prematurely ended.

4. Inclusion/Exclusion Criteria

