This study will include all patients over the age of 18 years who qualify for a pterional approach for their neurosurgical pathology. This will be determined by a clinical exam and plan by [name].

We will not include patients from protected populations, such as inmates or children. Patients will not be excluded on the basis of pregnancy.

5. Drugs/ Substances/ Devices

- a. The rationale for choosing the drug and dose or for choosing the device to be used. **N/A**
- b. Justification and safety information if FDA approved drugs will be administered for non-FDA approved indications or if doses or routes of administration or participant populations are changed. **N/A**
- c. Justification and safety information if non-FDA approved drugs without an IND will be administered. **N/A**

6. Study Statistics

- a. Primary outcome variable.
The primary end point and outcome variable will be the CT quantitative evaluation of TH. The pre and post operative CT scans will be analyzed by the same volume dimensional analysis which has been previously standardized by the lead authors' prior study on TH and cranioplasties (8). Percent change and volume analysis as compared to the non operated temporal region in a two dimensional and three dimensional view will be the primary outcome variable.
- b. Secondary outcome variables.
Secondary variables will include patient satisfaction for aesthetic results. Patients will be asked to rate their satisfaction of their aesthetic result on a scale from 1 to 10.

Date: 10/24/2017
Principal Investigator: [name]
Application Number: IRB00120812

- c. Statistical plan including sample size justification and interim data analysis.
A sample size of 30 patients was calculated (alpha error of .05 and a statistical power of 0.80) in order to detect a significant difference in post-operative TH in the 2 different surgical techniques. A paired Student t-test will be used to compare the degree of TH on the control side with the operated side. For the categorical data, a Fisher test and chi square test will be utilized. Differences less than 0.05 will be considered significant.
- d. Early stopping rules.
The study will be stopped early if patients with a certain type of TMS have favorable results.

7. Risks

- a. Medical risks, listing all procedures, their major and minor risks and expected frequency.
 - 1. There are no added risks to this study
- b. Steps taken to minimize the risks. **N/A**

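### Section 3.b leaves the whole study unblinded for a reason that concerns only the surgeon, so the patient's own satisfaction rating (6.b) could reflect expectation about the assigned closure.

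*Combined protocol and SAP*

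**What the plan says.** **Blinding (section 3.b).** "There will be no blinding of the study as the operating surgeon will need to know which operation to perform". No other reason is given, and patients and whoever collects their ratings are not mentioned separately.

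**Allocation (section 3).** Once the patient has agreed to take part, "randomization will take place by a coin flip". The text does not say who flips the coin, whether the patient is present, or whether the patient is told the result.

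**Secondary outcome (section 6.b).** "Secondary variables will include patient satisfaction for aesthetic results". The measurement is one item: "Patients will be asked to rate their satisfaction of their aesthetic result on a scale from 1 to 10". No time point is set for it. Section 6.c names a paired t-test of operated against control side, and Fisher and chi-square tests for categorical data. It states no between-arm test of the rating.

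**Primary outcome (section 6.a).** "The primary end point and outcome variable will be the CT quantitative evaluation of TH". This is an imaging measurement, not a patient report.

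**The two closures (sections 2 and 3).** Both groups have the traditional pterional approach, for which section 2 describes one incision. They differ in how the temporalis is handled and resuspended: "Either the entire temporalis muscle can be elevated or a cuff of temporalis muscle can be left on the cranium". One group is resuspended to the cuff, the other to a bone plate.

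**The concern.** Section 3.b asks for a justification for blinding or not blinding the trial, and the answer covers one person. A surgeon's need to know the operation does not mean that the patient must know it. Here the patient is also an assessor, because the satisfaction score is the patient's opinion of the result.

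A single subjective item is open to expectation. Suppose patients know their closure and, for whatever reason, tend to think one of the two is better. Mean ratings could then differ between arms although the aesthetic results are the same. The analysis could not separate that difference from a real one. It is also hard to repair later, because disclosure cannot be undone.

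At stake is the interpretation of the only patient-reported outcome the plan names, in a trial that section 1 introduces by the physical and emotional effect of hollowing on patients.

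**Working it through.** **Step 1: does the stated reason cover the patient?** Section 3.b gives the surgeon's need to know. Section 6.b makes the patient the rater. Side by side, the reason does not reach the rater, and no other section withholds the assignment from patients.

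**Step 2: could patients be kept unaware?** The approach and the described incision are common to both arms. The difference is at the temporalis muscle, its cuff and a bone plate that serves for fixation. Nothing described would let the scar reveal the arm. Withholding the assignment therefore looks feasible, although the document does not discuss it.

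**Step 3: the plan's own figure.** Section 6.c states: "A sample size of 30 patients was calculated (alpha error of .05 and a statistical power of 0.80". It gives no effect size or SD, so 30 cannot be reproduced. Reading 30 as a total with 15 per arm, the implied standardised difference (two-sided, normal approximation) is

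d = (1.960 + 0.842) × √(2/15) = 1.02.

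The t-based value is 1.06. This figure concerns hollowing, not satisfaction, and the present point does not depend on it.

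**Step 4: how far could expectation move the error rate?** This is an illustration.

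- From the plan: 30 patients in two groups and a 0.05 significance level.
- Assumed: exactly 15 per arm, which a simple coin flip does not guarantee.
- Assumed: a two-sided two-sample t-test on the rating, which the plan does not state.
- Assumed: no true difference, an SD s of 1.5 to 2.5 points, and an expectation shift b of 0.5 to 1.5 points between arms.

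With d = b/s, the test statistic follows a noncentral t distribution with 28 degrees of freedom and noncentrality δ = d × √(15/2) = 2.739d. The critical value is 2.048, and the false-positive rate is P(|T| > 2.048).

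For b = 1 and s = 2: d = 0.50, δ = 1.369, rate 26.2%.

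| Shift b (points) | SD 2.5 | SD 2.0 | SD 1.5 |
|---|---|---|---|
| 0 | 5% | 5% | 5% |
| 0.5 | 8.3% | 10.1% | 14.3% |
| 1.0 | 18.5% | 26.2% | 42.2% |
| 1.5 | 35.5% | 50.9% | 75.3% |

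Any non-zero shift raises the rate above 5%. How far depends heavily on two quantities that the document does not give.

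**The case against.** The strongest reply is that the bias needs two conditions, and the document establishes neither. Patients must know their arm, and their beliefs must favour one closure on balance.

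On the first, a reader might infer that patients are told their assignment. The document says only that the study is unblinded. The consent pages are not in the text available for review, so what patients hear cannot be judged.

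On the second, a reader might infer that expectation favours a particular arm. It is hard to see which. Section 2 lists the closures as alternatives, section 3 describes both arms as traditional, section 3.d treats some form of suspension as standard care, and section 8 (Benefits) leaves open whether either type helps. If beliefs are absent or balanced, there is no systematic shift. This part of the reply stands: direction and size are unknown, and the table is not an estimate for this trial.

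Three other limits also stand:

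- The wording of 6.b leaves the secondary list open, so satisfaction is the only secondary outcome named, not necessarily the only one.
- A reader might infer that the rating will decide whether a CT difference matters to patients. Section 6 gives it no such role.
- The error rates belong to a between-arm test that the two-arm design implies but section 6.c does not state.

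The reply does not remove the mismatch itself. The reason for no blinding is specific to the surgeon, a subjective rating is left exposed, and withholding the assignment from patients appears possible at little cost.

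**Conclusion.** The point holds as a limited, inexpensive design improvement. Section 3.b gives up patient blinding without a reason that applies to patients, and a between-arm comparison of their ratings could therefore reflect expectation. For a 1-point shift the illustrative false-positive rate runs from 18.5% to 42.2% as the assumed SD falls from 2.5 to 1.5. These figures rest wholly on the assumed shift, SD, equal arms and test.

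It would be too strong to say that the trial's main conclusion is at risk. The primary endpoint is measured on CT, and patient expectation does not plausibly alter it. It would also be too strong to say that the satisfaction result is biased: the document supports only that it could be.

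**What to change.** - **Section 3.b:** limit the no-blinding statement to the operating surgeon. Add that patients are not told their assigned closure until after the satisfaction rating, unless disclosure is needed for their care, and that the coin is flipped out of the patient's sight.
- **Section 6.b:** set the rating at the existing 6-month visit, before the CT is discussed with the patient. Without a time point, a rule to withhold the assignment until the rating cannot be applied.
- **Consent form:** align the wording, so that patients know the assignment is withheld and until when.

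The cost is a few sentences across these documents. There is no extra visit, procedure or staff, and neither the operations nor the sample size changes. The change belongs before enrolment. The small downside is that some patients may learn their arm or ask for it; record these cases and keep them in the analysis.

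If patients are not to be blinded, the minimum is to report satisfaction as an unblinded, exploratory outcome.

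### Section 6c claims 0.80 power for a difference between the two techniques, but no test it names compares the randomised arms on the quantitative CT primary outcome

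*Combined protocol and SAP*

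**What the plan says.** All in the combined protocol and SAP:

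- **Section 1 (Objectives):** the aim is to "identify which patients undergoing a traditional pterional approach with 2 different surgical techniques for TMS will develop TH". The introduction likewise asks whether the two closure techniques differ in TH.
- **Section 3 (Study Procedures):** a coin flip assigns each patient to one of two groups, a muscle cuff or a bone plate. CT is done before surgery and at 6 months. Section 3b says the trial is not blinded.
- **Section 6a:** "The primary end point and outcome variable will be the CT quantitative evaluation of TH". Pre- and post-operative scans are both analysed, and the measure is described as "Percent change and volume analysis as compared to the non operated temporal region", in two and three dimensions.
- **Section 6c, sample size:** 30 patients, alpha 0.05, power 0.80, "in order to detect a significant difference in post-operative TH in the 2 different surgical techniques".
- **Section 6c, tests:** "A paired Student t-test will be used to compare the degree of TH on the control side with the operated side". Then: "For the categorical data, a Fisher test and chi square test will be utilized".

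No section names a two-sample t-test, ANCOVA, regression or any other comparison of the CT measure by arm.

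**The concern.** The power statement concerns a contrast between two independent groups of patients. The paired test concerns a contrast between two sides of the same head, so it asks whether hollowing occurs, not whether it depends on technique. Section 8 (Benefits) already treats TH as a recognised consequence of the surgery. A significant paired result could therefore do little more than confirm that.

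Three things are at stake:

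- A significant result from the named test could be reported as evidence about technique when it carries none.
- The 0.80 power is not tied to any named test of the question the trial was randomised to answer.
- The primary between-arm test is left open in an unblinded trial. Section 6a also leaves open percent change or volume, and 2D or 3D.

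**Working it through.** **1. The plan's own figure.** N=30 cannot be reproduced. Section 6c gives alpha and power, but no effect size, SD, event rates, sidedness or dropout, and does not say whether 30 is the total or per arm. One can only solve backwards for the standardised effect that gives 80% power.

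**2. Inputs.** From the documents: N=30, alpha 0.05, power 0.80, two parallel arms by coin flip. Assumed: 30 is the total (15 per arm), two-sided test, normal within-patient side differences with SD 1 in each arm, no dropout. Effects are in units of that SD.

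**3. Effects at which N=30 has 80% power** (noncentral t, with noncentrality λ):

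| Test | λ | Effect for 80% power |
|---|---|---|
| Paired, n=30 | d·√30 | 0.529 SD (average side difference) |
| Two-sample, 15/15 | d / √(1/15 + 1/15) | 1.060 SD (difference between arms) |
| Two-sample, 10/20 | d / √(1/10 + 1/20) | 1.124 SD |
| Two-sample, 30/30, if 30 is per arm | d / √(1/30 + 1/30) | 0.74 SD |

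The first two rows have nearly the same λ: 0.53 × √30 = 2.90 and 1.06 / √(2/15) = 2.90. The same N therefore fits either test, but for different effects. A between-arm difference of 0.53 SD would have only about 29% power at 15/15.

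For the coin flip, the probability of a 10/20 split or worse is 2 × Σ C(30, x) / 2³⁰ for x = 0 to 10, which is 0.099.

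**4. Paired test pooled over arms** (an assumption; 6c does not say). The table gives the probability of rejection. The column for arms that differ was simulated with 400,000 trials per scenario, using arm means 0 and 1.06, 0.27 and 1.33, and 0.47 and 1.53.

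| Average side difference | Identical techniques | Arms 1.06 SD apart |
|---|---|---|
| 0.53 SD | 80% | 72% |
| 0.8 SD | 98.8% | 97.7% |
| 1.0 SD | 99.96% | 99.9% |

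A two-sample test on the same data rejects in 5% and 80% respectively, in every row. At 0.53 SD the pooled paired test rejects less often when the techniques differ, because the arm difference inflates the pooled SD.

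**5. Paired test run within each arm** (n=15 each), identical techniques. If each test has power p, the chance that exactly one is significant is 2p(1 − p):

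- 0.53 SD: p = 0.481, so 2 × 0.481 × 0.519 = 0.50
- 0.8 SD: p = 0.821, so 2 × 0.821 × 0.179 = 0.29
- 1.0 SD: p = 0.949, so 2 × 0.949 × 0.051 = 0.10

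Reading one significant and one non-significant arm as a difference between techniques would thus be wrong in 10% to 50% of such trials, against a nominal 5%.

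**The case against.** **The comparison is planned; only its test is missing.** The purpose and the first sentence of 6c both commit the trial to comparing techniques. This stands as far as it goes: a reader might infer that the sponsor does not mean to compare the arms, and the documents do not support that. But 6c does name a test for the continuous outcome, and it is one that cannot deliver the comparison.

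**Fisher or chi-square may have been meant for the arms.** The trial title speaks of risk, Section 1 of who develops TH, and Section 8 (Benefits) of incidence. At 15 per arm, an exact calculation gives Fisher's test 82% power for assumed rates of 10% versus 65%, so N=30 could even fit a binary outcome. Yet 6c reserves these tests for categorical data, 6a makes the primary outcome quantitative, and no cut-off appears. A cut-off may exist in the cited prior study, which I have not seen. If so, the plan needs to state it.

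**Pooling over arms is not stated.** Correct, and the rates in step 4 depend on it. Step 5 covers the within-arm reading, which does not test the difference either.

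**Side-to-side contrast is a sensible measure.** Agreed, as a per-patient outcome. What is missing is its comparison between arms.

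**No blinding does not prove a data-driven choice.** Also correct. The documents leave the test open; they do not show that it would be chosen after seeing results.

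**Conclusion.** The point holds and must be fixed before the analysis. The contrast that 6c says is powered has no named test on the primary outcome, and the test that is named does not use the randomised arm, pooled or within arms. With identical techniques, the pooled test rejects in 80% of trials at an average side difference of 0.53 SD and 98.8% at 0.8 SD; separate within-arm tests disagree in 50% and 29%. The mismatch itself follows from the text alone. The rates rest on assumed normality, SD 1, 15 per arm, two-sided 0.05 and no dropout, because the documents give no SD or effect size.

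A reader might go further and infer that 30 is too few, or that it came from a paired formula. Neither is supported. N=30 fits about 0.53 SD for the paired test or about 1.06 SD between arms, and the plan does not say which test or effect was used.

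**What to change.** Replace the paired-test sentence in 6c with:

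*The primary analysis compares the two randomised groups on each patient's operated-versus-non-operated CT measure, as defined in 6a from the pre-operative and 6-month CT, with a two-sample t-test, and reports the between-group difference with its 95% CI.*

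Also:

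- Name which 6a measure is primary: percent change or volume, 2D or 3D.
- Keep the paired test, labelled as descriptive.
- State the test, the effect size and the meaning of N (30 in total or per arm) behind the sample size calculation.
- Restate the power for the between-arm test. With 15 per arm, two-sided 0.05 and no dropout, 80% power needs about 1.06 SD, or about 1.12 SD at a 10/20 split. A split that uneven or worse has about 10% probability.

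Adjusting for the pre-operative side asymmetry is optional. No gain from it should be quoted until the outcome scale (6-month value or change) and an assumed correlation are stated, because the gain depends on both.

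**Cost.** No new data are needed, since both CTs are already collected. It is a wording change if the sponsor accepts a detectable difference of about 1.06 SD, which may be less favourable than intended. For a smaller target, an unadjusted two-sample test at 80% power needs 26 per arm for 0.8 SD and 64 per arm for 0.5 SD.
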